#### **4.2. Participant Exclusion Criteria**

Participants meeting any of the following criteria are not eligible for study participation:

1. Any clinically significant underlying illness in the opinion of the Investigator.
2. Poor venous access.
3. Prior exposure to ARN-75039.
4. History of drug or alcohol abuse within 1 year of Screening in the opinion of the investigator, or a positive test for drugs of abuse or alcohol at Screening or Day -1.
5. Use of any prescription or over-the-counter (OTC) medications, including food supplements, vitamins, herbal medications (e.g., St. John's wort), and cannabis, with the exception of contraceptive medications and as needed (prn) acetaminophen or paracetamol (not exceeding 2 grams/day) within 7 days prior to study drug administration and through the Day 15 Discharge visit.
6. Any female who is pregnant or breastfeeding, or any female who is planning to become pregnant during the study and safety follow-up period.
7. Currently enrolled in another investigational device or drug study, or less than 30 days or 5 half-lives of the prior investigational agent (whichever is longer) or plans to enroll in another investigational device or drug study during the course of this study.
8. Inability to ingest all capsules of a multi-capsule dose within 5 minutes of ingestion of the first capsule.
9. Positive serology for hepatitis B virus (HBV), hepatitis C virus (HCV), or human immunodeficiency virus (HIV) at Screening; participants with adequately treated HCV are eligible for enrollment.
10. Consumption of Seville oranges, grapefruit or grapefruit juice within 72 hours prior to Day 1 or during the study.
11. History of malignancy, except adequately treated basal cell carcinoma or in situ carcinoma of the uterine cervix.

12. Smoking cigarettes, cigars, cigarillos or E-cigarettes
13. Any reason or condition that, in the investigator's opinion, may compromise study participation, present a safety risk to the participant, or may confound the interpretation of the study results.
14. A QT duration corrected for heart rate by Fridericia's formula (QTcF) > 450 millisecond (msec) based on either single or averaged QTcF values of triplicate ECGs obtained over a 3-minute interval (at Screening).
15. Blood product (including plasma) donation within 30 days before Screening.
16. Unwilling to consume a breakfast on study drug administration days.
17. History of:
  - Structural abnormality of the GI tract or a disease or history of a condition that can affect GI motility.
  - Inflammatory bowel disease (even if treated and currently in remission).
  - Diverticulitis or any other chronic condition such as chronic pancreatitis, polycystic kidney disease, ovarian cysts, endometriosis, lactose intolerance that can be associated with abdominal pain or discomfort and could confound the assessments in this trial.
  - Chronic idiopathic diarrhea.
18. Formally diagnosed colonic inertia or conditions that can be associated with constipation: pseudo-obstruction, colonic inertia, megacolon, megarectum, bowel obstruction, descending perineum syndrome, solitary rectal ulcer syndrome, systemic sclerosis, lower tract evacuation disorders, functional outlet delay (e.g., rectal prolapse, anismus, etc.).
19. Current active peptic ulcer disease (i.e., disease that is not adequately treated or stable with therapy.)
20. Potential central nervous system cause of constipation (e.g., Parkinson's disease, spinal cord injury, and multiple sclerosis).
21. Participant currently has both unexplained and clinically significant alarm symptoms (lower GI bleeding [rectal bleeding or heme-positive stool], iron-deficiency anemia or any unexplained anemia, or weight loss) or systemic signs of infection or colitis.
22. History of chronic/generalized pruritus and/or skin rash of unknown origins.
23. Participants with diagnosed Type 1 or Type 2 diabetes, or with a fasting blood glucose value > 125 mg/dL during the screening period.

#### **4.3. Participant Withdrawal Criteria**

Study drug dosing will be permanently discontinued in a participant if any of the following occurs:

- Participant experiences any study drug-related Grade > 1 TEAE.

- Participant experiences any study drug-related Grade > 1 adverse event of special interest (AESI) as per [Section 6.13.6](#).
- Participant withdraws consent.
- Physician decision
- Participant is non-compliant with study drug
- Participant becomes pregnant.
- Participant is unable to comply with the protocol requirements.
- Sponsor terminates the study.
- Study dosing cessation is mandated by a regulatory authority.

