- **End of Active Treatment (Day 15 Discharge Visit or Early Termination Visit):** Upon successful completion of active treatment, participants will be discharged from the study site on Day 15. The Day 15 Discharge Visit will include the completion of safety assessments, such as a physical examination, vitals, ECG recording, adverse event review, and clinical laboratory tests. Participants who complete both dosing days will be encouraged to complete all study visits. Participants who do not complete all study visits or terminate early from the study will be asked to complete the Early Termination Visit within 1 day after withdrawal from the study.
- **Day 36 Telephone Follow Up Phone Call:** Participants will be contacted by phone on Day 36—i.e., 28 days following the last study dose administered on Day 8. The purpose of this follow-up call is to assess for any adverse events.

If a participant has a study drug-related Grade > 1 TEAE during the Treatment Period, study drug dosing may be discontinued for that participant following discussion between the Investigator and Sponsor Medical Monitor. These participants will not be replaced. If a subject has a study drug-related Grade 1 TEAE during the Treatment Period, study drug dosing may also be discontinued for that subject per the Investigator's discretion. However, these subjects may be replaced at the Sponsor's discretion. Discontinued participants experiencing a study drug-related TEAE will be asked to complete follow up study visits through the Day 36 Phone Call Follow Up.

If a participant terminates early for a reason other than a study drug-related TEAE during the Treatment Period, the participant may be replaced. These participants will also be asked to complete follow up study visits through the Day 36 Phone Call Follow Up, unless they terminated their participation in the study prior to dosing. Study drug dose level modifications or dosing administration deviations outside the protocol-specified windows are not permitted during the Treatment Period.

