### **3.3. Number of Participants**

The sample size of 16 evaluable participants proposed for this study was not based on statistical analysis assessments but is judged to provide a sufficient dataset to be able to make direct comparisons in pharmacokinetic parameter estimates between the reference and test groups in this clinical study. Participants withdrawn due to a study drug-related Grade >1 TEAE will not be replaced. Participants who are withdrawn due to a study drug-related Grade 1 TEAE may be replaced. Participants who are withdrawn due to a reason other than a study drug-related TEAE during the Treatment Period may be as necessary to obtain 16 evaluable participants at the end of the clinical study.

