## **5.5. Individual and Study Stopping Rules**

### **5.5.1. Individual Stopping Rules**

Dosing of ARN-75039 will be permanently discontinued in a participant if any of the following occurs:

- Participant experiences any study drug-related Grade > 1 TEAE
- Participant experiences any study drug-related Grade > 1 adverse event of special interest (AESI)
- Participant withdraws consent
- Participant becomes pregnant
- Participant is unable to comply with the protocol requirements
- Sponsor terminates the study
- Study dosing cessation is mandated by a regulatory authority

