#### **6.12.6. Adverse Events of Special Interest (AESI)**

All AEs and SAEs that occur during the study will be reported and investigated.

However, because of observations of tachycardia, early GI symptoms in animal studies (e.g., severe malnutrition due to reduced food consumption and body weight loss observed in rats that received ARN-75039 at doses  $\geq 2\times$  the NOAEL), and skin symptoms (e.g., grade 2 pruritus), subjects in this study should be monitored for any new onset or worsening of elevated heart rate, GI and skin-related signs and symptoms.

An AESI may be serious or nonserious (e.g., meeting regulatory criteria definition). Such events will require further investigation to better characterize and understand them. Even if not meeting the “seriousness” criteria to be reported as SAE, these events must be assessed for severity per [Section 6.13.3](#) and relationship to study drug similarly as for SAEs ([Section 6.13.2](#)).

Any AESI deemed as related (e.g., definitely, probably, or possibly), greater than grade 1 or severe (if not included in the NCI CTCAE) may require discontinuation of dosing of ARN-75039 (and follow-up until resolution) per the discretion of the Investigator and Sponsor Medical Monitor.

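### The Protocol makes stopping after a drug-related Grade >1 TEAE or AESI mandatory in 4.3 and 5.5.1 but discretionary in the synopsis, 3.1 and 6.12.6, and no passage says which prevails

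*Protocol*

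**What the plan says.** Protocol 4.3 opens its list with "Study drug dosing will be permanently discontinued in a participant if any of the following occurs". The list includes "Participant experiences any study drug-related Grade > 1 TEAE" and "Participant experiences any study drug-related Grade > 1 adverse event of special interest (AESI) as per" a section numbered 6.13.6. Protocol 5.5.1, the individual stopping rules, opens with "Dosing of ARN-75039 will be permanently discontinued in a participant if any of the following occurs" and lists the same two triggers. Neither section has a discussion step or an exception.

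Protocol 3.1 says "If a participant has a study drug-related Grade > 1 TEAE during the Treatment Period, study drug dosing may be discontinued for that participant". In that section the decision comes once the Investigator and the Sponsor Medical Monitor have conferred. The Study Design part of the synopsis has the same rule. Protocol 6.12.6 says that a related AESI above Grade 1 "may require discontinuation of dosing of ARN-75039 (and follow-up until resolution) per the discretion of the Investigator and Sponsor Medical Monitor".

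On replacement, Protocol 3.3 says "Participants withdrawn due to a study drug-related Grade >1 TEAE will not be replaced". The synopsis, Protocol 3.1 and SAP 3.3 agree. SAP 3.2 lets the Sponsor replace any participant who cannot complete the sequence and does not carve out this group.

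**The concern.** A participant-level stopping rule should give one answer for one event. Here two sections require a permanent stop and three places leave it to judgement, and nothing states an order of precedence. The trigger is foreseeable: 6.12.6 itself mentions grade 2 pruritus.

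There is a second consequence for the analysis. Dosing is on Days 1 and 8. A participant stopped before the Day 8 dose never receives the other formulation and gives no within-subject comparison for the relative bioavailability analysis in SAP 4.6. The study is open label (Protocol 5.2), so a discretionary choice to stop or continue is made knowing which formulation was given in Period 1. Because this group is not replaced under Protocol 3.3 and SAP 3.3, the choice of rule can also decide whether 16 evaluable participants are reached.

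**Working it through.** **Side by side.** All five passages are current text.

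| Place | Event covered | Consequence |
|---|---|---|
| Synopsis, Study Design | related TEAE, Grade >1 | may stop, after discussion |
| Protocol 3.1 | related TEAE, Grade >1 | may stop, after discussion |
| Protocol 6.12.6 | related AESI, Grade >1 | may require a stop, at discretion |
| Protocol 4.3 | related TEAE or AESI, Grade >1 | permanent stop |
| Protocol 5.5.1 | related TEAE or AESI, Grade >1 | permanent stop |

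For TEAEs in general, the conflict is between the synopsis and 3.1 on one side and 4.3 and 5.5.1 on the other. Section 6.12.6 covers AESIs only, so it conflicts with the AESI items in 4.3 and 5.5.1.

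**Which actions comply.**
- Discuss, then stop permanently: allowed by the discretionary passages and required by 4.3 and 5.5.1. No breach.
- Discuss, then give the Day 8 dose: allowed by the discretionary passages, forbidden by 4.3 and 5.5.1. Breach.

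**Cross-reference.** Section 4.3 sends the reader to 6.13.6 for AESIs. The AESI section is 6.12.6; 6.13 is concomitant medication.

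**Pairs at risk.** Only a stop before the Day 8 dose breaks a pair. The documents give no rate of such events and no within-subject CV, and both documents say that 16 was not based on statistical assessments. There is therefore no stated figure to reproduce, and what follows is illustration.

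If the mandatory text is applied and a share p of participants has a related Grade >1 event before Day 8 (p assumed), expected complete pairs are 16(1 − p) and the chance of losing at least one is 1 − (1 − p)^16:

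| p (assumed) | Expected pairs | Chance of losing at least one |
|---|---|---|
| 5% | 15.2 | 56% |
| 10% | 14.4 | 81% |
| 20% | 12.8 | 97% |
| 30% | 11.2 | above 99% |

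Under the discretionary text the expected number lies anywhere between these values and 16.

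**Precision.** With n complete pairs split equally between sequences, SE = s·√(2/n), where s = √ln(1 + CV²), and the half-width of the 90% CI on the log ratio is t(0.95, n − 2)·SE. The t quantiles are 1.761 (n = 16), 1.782 (n = 14) and 1.812 (n = 12). For the same estimated variance, relative to 16 pairs:
- 14 pairs: √(16/14) × 1.782/1.761 = 1.069 × 1.012 = 1.08, so 8% wider.
- 12 pairs: √(16/12) × 1.812/1.761 = 1.155 × 1.029 = 1.19, so 19% wider.

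**Chance of meeting 80.00-125.00%, per metric.** Two one-sided tests at 0.05 (SAP 4.6), exact calculation integrating over the estimated variance, assumed true ratio 1, CV assumed:

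| CV | 16 pairs | 14 pairs | 12 pairs |
|---|---|---|---|
| 15% | 98.2% | 96.2% | 92.1% |
| 20% | 83.3% | 75.5% | 64.4% |
| 25% | 57.2% | 46.6% | 34.9% |
| 30% | 32.5% | 23.8% | 16.1% |
| 40% | 7.0% | 4.6% | 3.0% |

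At a true ratio of 0.95 and CV 25% the row becomes 50.4%, 41.4% and 31.4%.

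**The case against.** A reader might infer that sites cannot follow both rules, or that any action deviates from one section. The text does not support that: permission to stop includes stopping, so a site that discusses the case and then stops complies throughout. The conflict arises only when dosing continues.

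A reader might also infer a material loss of power. The documents do not support a size. Protocol 1.2.3 reports the drug-related gastrointestinal events at 2000 mg as all mild, and the dose here is 300 mg, so losses may be few or none. Grade 2 pruritus is mentioned without a rate. The table above is driven mainly by the assumed CV: at 30-40% the chance is low even with all 16 pairs. SAP 4.6 already allows for an unbalanced model, and there is no planned power to lose. SAP 3.2 might also restore lost participants, but it then sits awkwardly with SAP 3.3.

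The amendment summary lists changes to discontinuation wording for the synopsis, 3.1 and the AESI section and none for 4.3 or 5.5.1. That may explain how the mismatch arose. It does not set an order of precedence.

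These points limit the statistical argument. None removes the contradiction between current sections.

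**Conclusion.** The point stands as an internal inconsistency that is wrong as written. Its weight rests on the conflicting stopping rule, not on power. What is certain from the text is that giving the Day 8 dose under the discretionary passages breaches 4.3 and 5.5.1, and that a participant stopped before that dose yields no pair and is not replaced under Protocol 3.3 and SAP 3.3. How many pairs this affects cannot be derived. The 8% and 19% wider intervals suppose that 2 or 4 of 16 pairs are lost; the chances of meeting the limits also suppose a CV and a true ratio that the documents do not give. This review takes no view on which rule is right.

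**What to change.** - Reconcile the synopsis, 3.1, 4.3, 5.5.1 and 6.12.6 to one rule chosen by the sponsor and medical monitor. State it once and have the other places cross-refer to it.
- Correct the AESI cross-reference in 4.3 from 6.13.6 to 6.12.6.
- Align the replacement text in SAP 3.2 with SAP 3.3 and the Protocol.
- Notify the site.

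SAP section 3 says participants were randomized, although its tenses are mixed. If dosing is already complete, an amendment changes nothing for participants. The useful step is then to report, for each participant with a related TEAE above Grade 1, which rule was applied and whether the second dose was given.

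Cost: a protocol clarification or amendment, a small SAP edit and a site notice, or one listing in the study report. The planned analysis model does not change.

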## 5. TREATMENT OF PARTICIPANTS

### 5.1. Description of Study Drug

#### 5.1.1. Study Drug

ARN-75039 will be supplied to the clinical site in two formulations.

- Formulation A (reference) consists of 300 mg neat ARN-75039, which will be prepared by the onsite pharmacist during study conduct. The onsite pharmacist will dispense the specified weight of drug substance and will encapsulate the neat ARN-75039 in an HPMC capsule prior to oral dosing.
- Formulation B (test, tablet form) consists of 300 mg ARN-75039 with excipients in tablets, which is manufactured initially as a dry blend with 33.6% w/w ARN-75039 along with intragranular excipients including 33.6% Prosolv SMCC 90 LM (silicified microcrystalline cellulose), 1.0% Aerosil 200 (Fumed Silica), 2.4% Ac-Di-Sol SD-711 (Croscarmellose sodium) and 1% Magnesium stearate. Excipients do not have any pharmacological activity. The drug product was manufactured and prepared under current Good Manufacturing Practice (cGMP) regulations at PACE Life Sciences (Norristown, PA).

Both neat ARN-75039 in HPMC capsules and ARN-75039 with excipients in tablet form are administered orally.

### 5.2. Treatments Administered

This is an open label study.

As outlined in [Figure 1](#), participants will be randomized into either Sequence 1 or Sequence 2. In Sequence 1, participants will receive 300 mg neat ARN-75039 in HPMC capsules during Period 1. After undergoing a 7-day washout period, participants in Sequence 1 will then receive 300 mg ARN-75039 with excipients in tablet form during Period 2.

In contrast, participants randomized into Sequence 2 will receive 300 mg ARN-75039 with excipients in tablet form during Period 1. After undergoing a 7-day washout period, participants in Sequence 2 will then receive 300 mg neat ARN-75039 in HPMC capsules during Period 2.

Study drug is to be administered in the fed state, with participants served a standard meal (approximately 400–600 Calories), which must be fully consumed within 30 minutes prior to the scheduled study drug dose. Study drug will be administered with 240 mL, or the smallest amount of water needed to swallow all the capsules.

The reference drug product will be prepared by the onsite pharmacist or designee by dispensing the specified weight of drug substance and encapsulating it in an HPMC capsule prior to oral dosing. ARN-75039 drug substance and comparator drug product should be stored at 15–25°C. The comparator drug product (prototype 5) is manufactured initially as a dry blend with 33.6% w/w ARN-75039 along with extragranular excipients including 33.6% Prosolv SMCC 90 LM (silicified microcrystalline cellulose), 1.0% Aerosil 200 (Fumed Silica), 2.4% Ac-Di-Sol SD-711 (Croscarmellose sodium) and 1% Magnesium stearate. The material is dry blended for 10 minutes without magnesium stearate followed by 2 additional minutes of mixing with the

addition of magnesium stearate. The mix is added to Gerties Roller compactor whereby ribbons are generated with an average thickness of 1.75-1.92 mm. The ribbons are then granulated using a 20-mesh screen. To the dry granulated material additional intragranular excipients are added including 19.4% Prosolv, 2.4% Ac-Di-Sol SD-711 and 1.9% Magnesium stearate and the material added to Korsch XL100, 24 tablet press. After tablets are pressed, they are coated using 24" CompuLab Coater with 3.8% Opadry Titanium Free 276U110003 Green color and 1.0% Opadry II 85F19999 Clear Coat.

The PK of tablets having a highly similar formulation (Prototype 1 same excipients and dry blend step) was tested in dogs. The tablet formulation began with dry-blend including 40% ARN-75039, 40% Prosolv, 1.0% Aerosil 200, 2.5% Ac-Di-Sol SD-711 and 1.0% Magnesium stearate followed by extragranular excipients for tablet pressing of 12.0% Prosolv, 2.5% Ac-Di-Sol SD-711 and 1% Magnesium stearate. The formulation was changed to prototype 5 because picking was observed during tablet pressing of prototype 1. A 100 mg tablet of prototype 1 formulation and a prototype 5 formulation were orally delivered to dogs and compared to HPMC capsules filled with 100 mg neat ARN-75039. Mean PK values are presented in [Table 2](#).

**Table 2: Mean Pharmacokinetics of ARN-75039 100 mg Prototype 1 and Prototype 5 Tablets and HPMC Capsules**

Oral Dose	C max ng/mL	T max (h)	AUC 0-24 (ng/mL*hr)	C min 24 hr ng/mL (μM)	Clearance (mL/min/kg)	Vd (L/kg)
100 mg API Neat in HPMC capsule	4518	5	45453	369.1 (0.89)	4	4
100 mg tablet P1	5105	2	39211	335.6 (0.81)	4	7
100 mg tablet P5	5346	4	42542	399 (0.96)	5	-

Abbreviations: API = active pharmaceutical ingredient; HPMC = hydroxypropyl methylcellulose

Prototype 5 stability after one month at both long-term (25°C/60% RH) and accelerated (40°C/75% RH) stability is presented in [Table 3](#).

**Table 3: One-Month Stability of Prototype 5 Tablets**

Time Point		Long-term Stability (25°C/60%RH)	Accelerated Stability (40°C/75%RH)	Specification
Initial	--	100%		90–110% of Label Claim
1 Month	--	99.5%	100%	
Related Substances				
Initial	RRT 0.66	0.05%		

Report all impurities ≥ 0.05% area

Individual Unspecified Degradation Impurities NMT 0.5% area

Total Degradation Impurities NMT 5% area

	iPrBA	0.06% 		
	Total Impurities	0.0% 		
1 Month	RRT 0.53	0.05%	0.05%	--
	RRT 0.94	0.05%	<LOQ	--
	Total Impurities	0.1%	0.1%	--

---

Abbreviations: LOQ = limit of quantitation; NMT = not more than; RH = relative humidity; RRT = relative retention time

 iPrBA is a process impurity not a degradation impurity. Process impurities are reported but excluded from total degradation impurity calculations.

 Individual degradation impurities are reported to two decimal places. Total impurities are reported to one decimal place. RRT 0.66 rounds to 0.05% when reported to two decimal places but 0.0% when reported to one decimal place.

### **5.3. Selection and Timing of Dose for Each Participant**

Study drug is to be administered in the fed state, with participants served a standard meal (approximately 400–600 Calories), which must be fully consumed within 30 minutes prior to the scheduled study drug dose. Study drug will be administered with 240 mL, or the smallest amount of water needed to swallow all the capsules.

### **5.4. Methods of Assigning Participants to Treatment Groups**

To eliminate potential bias, participants will be randomly assigned to either Sequence 1 or Sequence 2. The study site will utilize the randomization result generated to administer the appropriate study drug formulation to participants in accordance with the Study Schema ([Figure 1](#)) and the Schedule of Assessments ([Table 1](#)).

## **5.5. Individual and Study Stopping Rules**

### **5.5.1. Individual Stopping Rules**

Dosing of ARN-75039 will be permanently discontinued in a participant if any of the following occurs:

- Participant experiences any study drug-related Grade > 1 TEAE
- Participant experiences any study drug-related Grade > 1 adverse event of special interest (AESI)
- Participant withdraws consent
- Participant becomes pregnant
- Participant is unable to comply with the protocol requirements
- Sponsor terminates the study
- Study dosing cessation is mandated by a regulatory authority

